### 10.2. Data Collection and Case Report Form Monitoring

Prior to CRF and chart review, the study monitor will confirm that each subject has signed a Health Insurance Portability and Accountability Act (HIPAA)-compliant consent form or a HIPAA supplement to the consent form.

All data will be collected using ProtocolFirst (P1) Electronic Data Capture (EDC) system. The

set-up of the Web-based system will be executed by P1. A completion guideline will be developed to provide guidance to study site personnel on how to record data in the electronic case report form (eCRF).

A detailed monitoring plan will be developed to ensure the quality of the data. The progress of the study will be monitored by on-site and telephone communications between the investigator and personnel from the sponsor and/or designee. On-site visits would be performed at intervals deemed necessary to ensure compliance with the study protocol, to review the subject CRFs against the source documents as described below, to ensure that adequate records of clinical study supplies are maintained and to assess the continued suitability of the site. The investigator will permit direct access to paper/electronic source data/documents. If access to electronic Medical Records not granted due to institution's policy, the investigator will print and provide paper source bounded and signed.

The eCRFs must be kept up-to-date, always reflecting the latest observations on the subjects enrolled in the study.

### 10.3. Study Files and Source Documents

The investigator must maintain adequate and accurate clinical study documentation to ensure protocol procedures were adequately performed and provide documentation that study data was appropriately collected and accurately entered into the eCRF. The investigator will ensure that all study files are maintained, including IRB-approved study protocol and amendments, IRB-approved consent forms, inventory records, and all other required regulatory documents.

All individual entries in the source need signature and date by the authors. All typed or dictated documents and computer printouts must be signed and dated by the investigator to confirm review. Preliminary and/or fax copies of laboratory reports must be initialed and dated, and need to be retained. Final laboratory reports should be signed and dated by the investigator to confirm review. Original laboratory reports should be kept in file.

The following are considered to be source documents, but not limited to:

- Medical charts, clinic charts, nurses' notes, medical correspondence regarding the subject;
- Subject progress notes;
- ECG tracing, X-ray reports, CT scans;
- Pathology reports;
- Quality of life questionnaires;
- Laboratory reports;
- Study worksheets; and/or
- Electronic (paperless) hospital reporting systems – the investigator must sign and date a hard copy of this data for this to be considered a source document.

---

#### 10.4. Data Validation

A detailed validation plan will be developed to ensure the quality of the data. The Web-based system will integrate data discrepancy management and resolution with audit trails. The CRF will be validated through extensive data checking and query processing capabilities. Capabilities will include generating open queries and routing answers.

#### 10.5. Data Analysis

##### 10.5.1. Samples for Analysis

###### *10.5.1.1. Intent-to-Treat Population*

The Intent-to-Treat (ITT) Population will be defined as all enrolled subjects.

###### *10.5.1.2. Safety Population*

The Safety Population will be defined as all enrolled subjects who received the Photofrin® injection.

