##### 10.5.3. Safety Analysis

Safety analysis will be performed on the Safety Population.

The number and percentage of subjects with normal and abnormal findings will be provided for each physical examination in a shift table comparing screening and the end of study evaluation.

Vital signs will be summarized descriptively (mean, standard deviation, median, minimum and maximum). Change from baseline will also be summarized.

Skin photosensitivity is an adverse event of special interest and will be summarized separately from other adverse events at each safety assessment. Changes in skin will be assessed by grade of erythema, edema and blistering. The data will be tabulated by CTCAE grade in the Dermatology/Skin category.

Descriptive statistics for each clinical laboratory test will be presented for the baseline and the end of study assessment. Change from baseline will also be summarized. According to the laboratory normal ranges, laboratory test results will be categorized as low (< lower limit of normal, LLN), normal (within normal range), and high (> ULN). Shift tables, comparing the distributions of these three categories at baseline versus the end of study assessment, will be presented.

---

Concomitant medications will be coded using the WHO Drug dictionary. Medications initiated prior to start of treatment and maintained during the study, or taken during the course of the study will be considered as concomitant medications. Concomitant medications will be summarized according to the preferred terms only.

Adverse events will be coded using the Medical Dictionary for Regulatory Activities (MedDRA). The number and percentage of subjects who experienced any AEs as well as serious AEs will be presented by system organ class (SOC) and by preferred term (PT) within SOC. All AEs will be similarly presented by intensity (mild, moderate, severe or using the CTCAE grading system) and by relationship to treatment (reasonable possibility/no reasonable possibility). One-sided 95% confidence limit will be computed for each AE percentage via exact binomial method (Clopper-Pearson, 1934).

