3. DATA ANALYSIS CONSIDERATIONS

3.1 Determination of Sample Size

This study is designed to assess the safety of PDT in subjects with solid lung tumors prior to surgical resection and to assess the lung tumor and healthy tissue response to PDT. The intent of this study is to enroll 10 subjects. This sample size has the following precision for estimation of rates of AE's of special interest (AESI). The following table shows historical AE rates for RFA ranging from <1 to $\sim50\%$.

AESI	Rate Observed with RFA				
Pneumothorax	11-52%				
Pleural effusion	6-19%				
Hemorrhage	6-18%				
Pulmonary artery pseudoaneurysm	0.2%				
Needle tract seeding	0.3-0.7%				
Cavitation	14%				
Bronchopleural fistula	0.6%				
Pneumonitis	0.4%				

The sample size of N=10 has precision for estimation of AE rates for estimates ranging from <0.01 to ~0.5 as shown in the following list. Precision is measured by 1-sided 95% upper confidence limit (CL) on the estimated AE rate via exact binomial distribution. PDT is expected to have lower AE rates than RFA, so, for example, for a RFA historical rate of 0.27 (27%), if no such AE's are observed on PDT, then the TRUE underlying PDT rate is lower than 0.27 with 95% confidence since the upper 95% CL is 0.26 - indicated by "*" in the list below.

No. of AESIs	Rate	Upper 1-sided 95% confidence limit
0	0.00	0.26*
1	0.10	0.39
2	0.20	0.51
3	0.30	0.61
4	0.40	0.70
5	0.50	0.78

The study will be suspended and re-evaluated from a safety standpoint if 20% of the subjects experience a serious adverse event that is related to PDT.

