5. STATISTICAL METHODOLOGY

5.1 General Considerations

All statistical evaluations will be conducted using SAS® version 9.4 or higher (SAS® Institute, Cary, North Carolina). All tables, figures and listings will be produced in landscape format.

In general, all data will be listed by subject and visit/time point where appropriate. The total number of subjects under the stated population (N) will be displayed in the header of summary tables.

Data will be summarized using descriptive statistics for continuous variables. Unless otherwise specified, descriptive statistics will include number of subjects, mean, standard deviation, minimum, median and maximum. In case of n<2, where n indicates the number of evaluable subjects at the particular time point, the standard deviation will be empty. The statistic "Missing" will also be presented as the number of missing entries/subjects, if any at that visit/timepoint, and presented as a summary statistic only when non-zero. The minimum and maximum statistics will be presented to the same number of decimal places as the original data. The mean and median will be presented to one more decimal place than the original data, whereas the standard deviation will be presented to two more decimal places than the original data.

In summary tables of categorical variables, counts and percentages will be used. The count [n] indicates the actual number of subjects with a particular value of a variable or event, which should always be less than or equal to the total number of subjects with non-missing value of the variable or event [M]. Percentage will be obtained by: % = (n/M)*100. Unless otherwise stated, all percentages will be expressed to one decimal place.

In by-visit summary tables only scheduled visits/timepoints will be summarized. In listings all visits and timepoints with any data collected, including both scheduled and unscheduled ones and early termination visits, will be included.

The closest non-missing measurement (whether from scheduled or unscheduled visit) taken prior to the administration of the study drug (PHO) will be considered as the baseline value. The change from baseline values will be derived for each subject as the post-baseline evaluation minus the baseline evaluation.

Study days will be calculated as the number of days from the date of the study drug administration:

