5.4 Analysis Methods

5.4.1 Study Subjects Disposition

Subject disposition will be summarized by presenting the number of subjects who were enrolled, were included into the ITT and safety populations, received PDT, underwent planned surgery, completed the study and prematurely discontinued with breakdown by the reason for early discontinuation. The analysis will be based on all enrolled subjects.

A listing will be presented to describe whether the subject completed the study, date of completion or early withdrawal, and the reason for early discontinuation, if applicable. A listing will also be provided to describe if the subject meets all inclusion/exclusion criteria. The reason for entry criteria violation, if any, will be presented.

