5.4.11 Safety Analysis

All safety data will be listed and tabulated. The analysis will be performed on the Safety population.

Safety parameters include adverse events, laboratory data, physical examination findings, vital signs and concomitant medications.

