5.4.11.1 Adverse Events

Adverse Events will be coded using the Medical Dictionary of Regulatory Activities (MedDRA version 20.0) AE coding system for purpose of summarization.

Events collected at the "NCS Events" CRF page will be summarized together with Adverse Events, but excluded from analyses by CTCAE grade and relationship to study drug, since these data points are not captured for NCS events.

An AE will be defined as treatment-emergent (TEAE) if its date of onset is on or after the date of the study drug (PHO) administration.

An AE will be defined as treatment-related if its relationship to the study drug is recorded as "Reasonable Possibility" on the CRF.

An overall summary of number and percentage of subjects with at least one AE, TEAE, serious TEAE, treatment-related TEAE, serious treatment-related TEAE, TEAE leading to discontinuation and fatal TEAE will be presented.

A summary of the frequency (number and percentage of subjects) of TEAEs will be presented by system organ class and preferred term. One-sided 95% upper confidence limit will be computed for each AE percentage via exact (Clopper-Pearson) method for binomial proportion. Adverse events will also be analyzed by their CTCAE grade (1 to 5) and relationship to study drug (related or not related).

A subject experiencing the same AE multiple times will be counted only once for that preferred term. Similarly, if a subject experiences multiple AEs (preferred terms) within the same system organ class, then that subject will be counted only once for that system organ class. When summarizing by CTCAE grade and relationship, only event with highest grade or relationship will be counted. All AEs will be presented in alphabetical order of SOC and preferred terms.

Skin photosensitivity is an adverse event of special interest (AESI). Skin photosensitivity will be summarized separately by SOC and preferred term as well as by SOC, preferred term and CTCAE grade.

All information pertaining to adverse events noted during the study will be listed by subject, detailing verbatim term given by the investigator, preferred term, system organ class, start date, stop date, CTCAE grade, outcome, action taken and drug relatedness. Separate listings will be created for Serious TEAEs, TEAEs leading to study drug discontinuation and skin photosensitivity events.

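### Adverse-event rates for the PDT procedure have no denominator limited to subjects who reached the bronchoscopy; add a supplementary set

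*Protocol*

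**What the plan says.** Protocol 10.5.1.2 defines the Safety Population as "all enrolled subjects who received the Photofrin" injection, and SAP 5.2.2 repeats the definition. The only other population is ITT, all enrolled subjects, which is no narrower.

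Both documents run the safety analysis on the Safety Population alone: "Safety analysis will be performed on the Safety Population" (Protocol 10.5.3) and "The analysis will be performed on the Safety population" (SAP 5.4.11). SAP 5.4.11.1 adds the interval: "One-sided 95% upper confidence limit will be computed for each AE percentage via exact (Clopper-Pearson) method for binomial proportion".

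The sample-size text gives the limit its meaning. For an illustrative RFA rate of 27% and no observed events, SAP 3.1 concludes: "then the TRUE underlying PDT rate is lower than 0.27 with 95% confidence since the upper 95% CL is 0.26". Protocol 10.1 says the same. The AESIs listed there include pneumothorax, pleural effusion and hemorrhage, with rates seen after RFA.

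Exposure to the procedure is recorded but not used as a denominator. The disposition table counts subjects who "received PDT, underwent planned surgery" as separate milestones (SAP 5.4.1), and light-application details are listed (SAP 5.4.7).

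**The concern.** Protocol 1.3 describes PDT as light given after a photosensitizer, so an injection with no light is not PDT in the protocol's own terms. The light session comes 40 to 50 hours after the injection (Protocol 3.1). It needs a return visit, general anesthesia or deep sedation, and navigated bronchoscopy (Protocol 5.2.1.2). Protocol 4.7 allows a subject to leave the study for an adverse event, a new illness or personal reasons, which could happen in that interval.

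A subject who leaves before the bronchoscopy stays in the denominator but was never at risk of a pneumothorax caused by the bronchoscope or tissue injury caused by light. For those events the percentage is diluted and the upper limit is too low. Safety is the primary objective and the limits are to be read as statements about PDT, so with about 10 subjects even one such case is visible in the result.

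**Working it through.** **Inputs**
- Planned size: 10 subjects (Protocol 10.1, SAP 3.1).
- Limit: one-sided 95% upper, exact binomial (SAP 5.4.11.1, Protocol 10.5.3).
- Percentage: "Percentage will be obtained by: % = (n/M)*100" (SAP 5.1), where M is the number of subjects with a non-missing value.
- Injected subjects who never reach the bronchoscopy: not given. I assume 0 to 3 of 10.

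**Step 1: reproduce the plan's table.** For x events in n subjects the upper limit is the 0.95 quantile of Beta(x+1, n−x). For x = 0 this is 1 − 0.05^(1/n). With n = 10 and x = 0 to 5 it gives 0.2589, 0.3942, 0.5069, 0.6066, 0.6965 and 0.7776. Rounded, these are the printed 0.26, 0.39, 0.51, 0.61, 0.70 and 0.78, so the table is correct for 10 subjects at risk.

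**Step 2: does the percentage formula already remove these subjects?** No. A subject without an adverse event has a known value (no event), not a missing one, so M still counts everyone injected.

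**Step 3: recompute on the subjects at risk.** For zero events: 1 − 0.05^(1/9) = 0.283, 1 − 0.05^(1/8) = 0.312, 1 − 0.05^(1/7) = 0.348.

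| At risk | Limit, 0 events | Limit, 1 event | Limit, 2 events | Percentage, 1 event |
|---|---|---|---|---|
| 10 | 0.259 | 0.394 | 0.507 | 10.0% |
| 9 | 0.283 | 0.429 | 0.550 | 11.1% |
| 8 | 0.312 | 0.471 | 0.600 | 12.5% |
| 7 | 0.348 | 0.521 | 0.659 | 14.3% |

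**Step 4: confidence attached to the limit computed on 10.** If only n were at risk, the zero-event limit of 0.2589 carries confidence 1 − (1 − 0.2589)^n: 0.950 for n = 10, 0.9325 for 9, 0.909 for 8 and 0.877 for 7.

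**Step 5: which event defines being at risk?** In Protocol 5.2.1.2, sedation, bronchoscopy, the ultrasound probe and fiber insertion all come before the laser is switched on. Suppose all 10 subjects are taken to bronchoscopy and one procedure is stopped for pneumothorax before light.
- Safety Population: 1/10, limit 0.394.
- Subjects with any light delivered: 0/9, limit 0.283. The event has disappeared.
- Subjects with bronchoscopy started: 1/10, limit 0.394. The event is kept.

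For procedural events the at-risk set must therefore start at the bronchoscopy, not at the light.

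**The case against.** The strongest reply is that the Safety Population is a sound choice. The treatment course begins with the injection, event rates among all who start it are a legitimate safety target, and the injected set is right for skin photosensitivity, the only AESI that the analysis sections single out for separate summary. This stands, and it is why the point asks for an addition and not a replacement.

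A reader might infer that the planned pneumothorax or hemorrhage percentages are biased downward as they stand. The documents do not support that. SAP 5.4.11.1 tabulates every event with onset on or after the injection date, whatever its cause. Lung resection follows on Days 13 to 18, and follow-up runs to 90 days after surgery. Nothing says that a subject who misses PDT also misses surgery, so such a subject can still have a surgical pneumothorax. Dilution is established only for events caused by the bronchoscopy or the light.

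A reader might also infer that one untreated subject overturns the plan's claim, because 0.283 exceeds 0.27. The 0.27 is offered as an example. It is not the listed rate for any AESI (pneumothorax is 11-52%), and no success criterion or decision depends on it. Nor does SAP 5.4.11.1 say that events nobody experienced will be given a row with a limit.

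Two further replies have some force. If placing the fiber in the lesion fails, Protocol 5.2.1.2 accepts placement next to the tumor, which closes one route to missing light. And with about 10 subjects, a reader could recompute rates from the disposition counts and listings. No such analysis is planned, however, and a denominator chosen after the data are seen carries less weight than a prespecified one.

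**Conclusion.** The point holds as a limited, inexpensive improvement to the primary safety analysis. For events caused by the bronchoscopy or the light, each injected subject who never reaches the bronchoscopy makes the reported rate and upper limit too low. The zero-event limit should be 0.283 with one such subject, 0.312 with two and 0.348 with three, against 0.259 on all 10.

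This rests on the assumed 0 to 3 untreated subjects and on 10 injected. If every injected subject goes to bronchoscopy, the procedural figures do not change. The documents do not support calling the Safety Population wrong, or claiming a known direction of bias in the all-cause rates.

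**What to change.** - Keep the Safety Population as the primary set for all adverse events and for photosensitivity.
- Define in the SAP a supplementary set: injected subjects in whom the PDT bronchoscopy was started, whether or not light was delivered. Aborted procedures and their events then remain in the analysis.
- Repeat the AE table with one-sided exact 95% upper limits on that set for the procedural AESIs: pneumothorax, pleural effusion and hemorrhage.
- Use any light delivered as the denominator only for events attributable to light, and state how that attribution is made.

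The supplementary set corrects the denominator only. It does not separate procedural from surgical events, so the table footnote should say that all-cause events are counted.

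The cost is one or two definitions and one repeated table. Light details are already collected on the CRF (SAP 5.4.7); the sponsor should confirm that the start of the bronchoscopy is recorded too. Upper limits will be slightly higher if any subject is not treated.

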##### 10.5.2. Analysis of Baseline, Disposition, and Demographic Data

Baseline and subject demographic information will be summarized using descriptive statistics (mean, median, standard deviation, minimum, maximum) for quantitative variables (e.g., weight) and counts and percentages for categorical variables (e.g., sex). Subject demographics and selected baseline information will be summarized for the Safety Population.

The frequency and percent of subjects who enroll in the study, complete the study, or discontinue the study prior to completion will be summarized.

##### 10.5.3. Safety Analysis

Safety analysis will be performed on the Safety Population.

The number and percentage of subjects with normal and abnormal findings will be provided for each physical examination in a shift table comparing screening and the end of study evaluation.

Vital signs will be summarized descriptively (mean, standard deviation, median, minimum and maximum). Change from baseline will also be summarized.

Skin photosensitivity is an adverse event of special interest and will be summarized separately from other adverse events at each safety assessment. Changes in skin will be assessed by grade of erythema, edema and blistering. The data will be tabulated by CTCAE grade in the Dermatology/Skin category.

Descriptive statistics for each clinical laboratory test will be presented for the baseline and the end of study assessment. Change from baseline will also be summarized. According to the laboratory normal ranges, laboratory test results will be categorized as low (< lower limit of normal, LLN), normal (within normal range), and high (> ULN). Shift tables, comparing the distributions of these three categories at baseline versus the end of study assessment, will be presented.

---

Concomitant medications will be coded using the WHO Drug dictionary. Medications initiated prior to start of treatment and maintained during the study, or taken during the course of the study will be considered as concomitant medications. Concomitant medications will be summarized according to the preferred terms only.

Adverse events will be coded using the Medical Dictionary for Regulatory Activities (MedDRA). The number and percentage of subjects who experienced any AEs as well as serious AEs will be presented by system organ class (SOC) and by preferred term (PT) within SOC. All AEs will be similarly presented by intensity (mild, moderate, severe or using the CTCAE grading system) and by relationship to treatment (reasonable possibility/no reasonable possibility). One-sided 95% confidence limit will be computed for each AE percentage via exact binomial method (Clopper-Pearson, 1934).

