#### 4.3.2. Exclusion Criteria

Potential subjects who meet any of the exclusion criteria will not be allowed to enroll into the study.

1. Subject diagnosed with small cell lung cancers or carcinoid tumors.
2. Subject has a primary or metastatic lung tumor located within 2 cm of the proximal bronchial tree or within 2 cm of a major structure (e.g., aorta, heart, trachea, pericardium, superior vena cava, pulmonary artery, pulmonary vein, esophagus, spine).
3. Subject has a primary or metastatic lung tumor near the vertebral body.
4. The tumor invades a major blood vessel.
5. Subject with concurrent non-solid malignancy.
6. Subject has had previous direct radiation treatment (other than mediastinal radiation) on the tumor scheduled for resection.
7. Subject has had chemotherapy in the last four weeks.
8. Subject has received prior PDT on the tumor scheduled for resection during 3 months prior to the date of the ICF signature.
9. Subject with blood parameters of Grade 3 or higher on the Common Terminology Criteria for Adverse Events (CTCAE) 5-point scale; parameters of Grade 2 will be excluded if judged clinically significant by the investigator.
10. Subject with known porphyria or known hypersensitivity to Photofrin® or porphyrin-like compounds or to any of its excipients.
11. Subject with a coexisting ophthalmic disease likely to require slit-lamp examination within the next 90 days.
12. Subject with any acute or chronic medical or psychological illnesses as judged clinically significant by the investigator to preclude bronchoscopy procedures.
13. Female subject who is breastfeeding or intends to breastfeed during the study.
14. Subject who participated within the last 30 days, participates or intends to participate in another investigational study (other than observational studies) during the study.

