## 8.3. Laboratory Abnormalities

During the course of the study, the investigator will be required to comment on any laboratory values outside the normal reference range. A laboratory abnormality should be regarded as an AE and recorded on the Adverse Event Form of the CRF if, per the investigator's judgment, the value is significantly worse than at pretreatment (where "significantly worse" is defined as Grade 3 or 4 by the CTCAE) and has been confirmed by repeat testing, when applicable. In addition, a clinically significant abnormal laboratory test value discovered after ICF signature and that was not previously known should be considered as an AE.

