4. PRIMARY AND SECONDARY ENDPOINTS

4.1 Primary Endpoints

The primary endpoints are safety assessments:

- incidence of adverse events and serious adverse events
- laboratory data
- physical examination
- vital signs
- concomitant medication

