5.4.11.2 Clinical Laboratory Parameters

Samples will be obtained for the clinical laboratory tests at the following time points: Screening, Hospital Discharge (Day 5) and Study Exit visits.

The following tests will be performed:

- Chemistry: Glucose (random), Blood urea nitrogen, Sodium, Potassium, Chloride, Creatinine, Alkaline Phosphatase, Aspartate Aminotransferase, Alanine Aminotransferase, Total bilirubin, Albumin, Total protein.
- Hematology: Hemoglobin, Hematocrit, White blood cell, Red blood cell, Platelet count, Prothrombin time

Additionally, samples for Serum β -HCG pregnancy test will be collected from women of childbearing potential only at Screening, Day 43-48 visit and Study Exist visit.

Laboratory results for chemistry and hematology as well as changes from baseline will be summarized descriptively by visit. Only subjects with both non-missing baseline and time point values will be summarized at each time point.

Shifts among normal, low and high results (as determined by laboratory normal ranges) from baseline to last available post-baseline assessment will be summarized.

All individual subject clinical laboratory results will be presented in listings by subject and visit. Results of the pregnancy test will be listed.

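### The laboratory shift table uses only low, normal and high, so same-direction worsening from an abnormal entry value is counted as no shift

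*Protocol*

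**What the plan says.** Protocol 10.5.3 classifies each result against the laboratory's normal range: "laboratory test results will be categorized as low (< lower limit of normal, LLN), normal (within normal range), and high (> ULN". The shift table is then built by "comparing the distributions of these three categories at baseline versus the end of study assessment". SAP 5.4.11.2 has the same three classes with a slightly different end point: "Shifts among normal, low and high results (as determined by laboratory normal ranges) from baseline to last available post-baseline assessment will be summarized". No laboratory table by CTCAE grade is planned in either document, and SAP Section 6 records no departure from the protocol's analyses.

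The trial does use CTCAE for laboratory values in two other places.

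- **Eligibility (protocol 4.3.2, criterion 9).** The excluded subject is a "Subject with blood parameters of Grade 3 or higher on the Common Terminology Criteria for Adverse Events (CTCAE) 5-point scale". For the next grade down, "parameters of Grade 2 will be excluded if judged clinically significant by the investigator". Grade 1 values, and Grade 2 values not so judged, can therefore be present at entry.
- **Laboratory adverse events (protocol 8.3).** A value is recorded as an adverse event if the investigator judges it significantly worse than before treatment, which "is defined as Grade 3 or 4 by the CTCAE", with confirmation by a repeat test when applicable. A second route covers clinically significant abnormal values that were not known before.

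SAP 4.1 names "laboratory data" among the primary endpoints. Apart from the shift table, SAP 5.4.11.2 plans descriptive summaries of values and of change from baseline by visit, and a listing of every result.

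**The concern.** A shift table is meant to show how many subjects moved, and in which direction. Here a subject who is already outside the range at baseline has no further cell to move to on that side. Same-direction worsening leaves the subject on the diagonal, together with subjects whose values did not change.

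This is the only categorical analysis of the laboratory results themselves, and laboratory data form part of the primary endpoint of a safety study. The graded scale is used at entry and in the adverse event rule but not in this table. The table therefore cannot separate stable from worsening abnormality in the subjects who entered with one. The limitation comes from the classes, so it is the same whether the follow-up value is the end-of-study one (protocol) or the last available one (SAP).

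**Working it through.** The plan gives no figure on this point to reproduce. The precision table in protocol 10.1 concerns adverse event rates and has no bearing on it. The check is an enumeration.

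**Inputs**

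- Grades allowed at entry: 0, 1, and 2 when not judged clinically significant (protocol 4.3.2, criterion 9).
- Shift classes: low, normal, high (protocol 10.5.3; SAP 5.4.11.2).
- Laboratory adverse event grade rule: Grade 3 or 4, subject to investigator judgment and, when applicable, a repeat test (protocol 8.3).
- Assumption: Grades 1 to 4 of a test lie on the same side of the normal range. The documents give neither the CTCAE version nor the grade thresholds, so this cannot be checked test by test.

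**Worsening in the same direction from an abnormal entry value**

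| Path | Grades worse | Low/normal/high table | Protocol 8.3 grade rule |
|---|---|---|---|
| 1 to 2 | 1 | no shift | does not apply |
| 1 to 3 | 2 | no shift | applies |
| 1 to 4 | 3 | no shift | applies |
| 2 to 3 | 1 | no shift | applies |
| 2 to 4 | 2 | no shift | applies |

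- Hidden in the planned shift table: 5 of 5 paths. The largest is 4 − 1 = 3 grades.
- Shown by a CTCAE-grade shift table: 5 of 5.
- Ending at Grade 3 or 4, so within the 8.3 grade rule: 4 of 5. These include all three multi-grade paths (1 to 3, 1 to 4, 2 to 4).
- Outside the 8.3 grade rule: 1 of 5, the path from 1 to 2.

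Worsening from a normal entry value is not affected: under the same assumption, any move from Grade 0 crosses the range limit and appears as a shift.

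**What the other outputs show**

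- *Adverse event table.* It can show the four paths that end at Grade 3 or 4, by CTCAE grade (SAP 5.4.11.1), if the investigator records them.
- *Descriptive summaries.* The minimum and maximum change show the largest movement for each test. They do not show how many subjects rose in grade.
- *Listings.* Every value is there, but ungraded as specified. SAP 5.4.11.2 names 12 chemistry and 6 hematology tests, so 18, at three scheduled times. With 10 subjects who all complete, that is 10 × 18 × 3 = 540 scheduled values, and the reader would have to grade the gradable ones by hand.

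**The case against.** The strongest reply is that little is lost. Because Grade 3 and above is excluded at entry, every multi-grade worsening ends where protocol 8.3 sends it to the adverse event form, and 8.3 also asks the investigator to comment on any value outside the reference range. For the path from Grade 1 to 2 there are partial routes. Protocol 8.2 makes a worsened pre-existing condition an adverse event, and protocol 8.4.1 has adverse events drawn from CRF data, including laboratory values. SAP 5.4.11.1 summarizes events from the NCS Events page together with adverse events. All results are listed, and about 10 subjects can be read one by one.

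Much of this stands, and it limits the point. A reader might infer that multi-grade worsening would go unreported; the documents do not support that, because 8.3 and the listings cover it. Nor is there a contradiction: no section promises a graded laboratory table, and the planned one does show movement across the normal range.

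The reply does not remove the point. The 8.3 route rests on judgment and, when applicable, a repeat test. Protocol 8.2 helps only if the site treats the value as a pre-existing medical condition. Events from the NCS page carry no CTCAE grade and are left out of the analyses by grade. None of these routes gives a count of subjects whose grade rose.

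**Conclusion.** The point holds as a cheap improvement of low severity. The planned table records no shift for all five same-direction worsening paths that eligibility allows from an abnormal baseline. Four of them have a second route through protocol 8.3. The path from Grade 1 to 2 of a known abnormality falls outside that grade rule and may be visible only in the listings and the change-from-baseline summaries.

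The count of paths rests on grades lying on one side of the normal range. For a test whose grades are not tied to the range limits, the number of hidden paths could differ.

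The count says nothing about frequency. A reader might want a probability that worsening is hidden, but that needs the share of subjects abnormal at entry for each test and the number who worsen. The documents give neither, so no such figure is offered.

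**What to change.** In SAP 5.4.11.2, keep the low/normal/high table and add a second one. For each test that CTCAE grades, and separately for the low and high directions, tabulate the shift in CTCAE grade from baseline to the worst post-baseline value, taken from Day 5, study exit or any unscheduled result. Using the worst value also brings in a Day 5 change that has resolved by exit. State the CTCAE version, and record the addition in SAP Section 6, which now reports no changes.

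The graded table should be added, not substituted. Where a grade threshold does not coincide with a range limit, replacing the present table could hide normal-to-abnormal shifts that it now shows.

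No new visit, sample or data item is needed. The cost is one derived variable, a somewhat larger table set and a CTCAE version fixed for programming.
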